### 11 Concomitant Medications and Exposures

#### 11.1 Prior Medications

All medications and herbal supplements used by a patient within 14 days prior to screening are recorded in the medical history. Dose, frequency, and purpose of use are recorded, as best the volunteer can recall.

### 11.2 Concomitant Medications

The Investigator notifies the Medical Monitor regarding all medications taken by a subject during study participation, for treatment of Adverse Events or pre-existing conditions.

#### 12 TREATMENT OF SUBJECTS AND CONDUCT OF STUDY

Subjects can be screened up to seven days to 4 hours before treatment. Subjects who have been found eligible for the study based on the inclusion and exclusion criteria will have the study explained in detail. If the subject decides to participate in the study, the subject will be given a study specific ICF to sign. Only after the subject undergoes the informed consent process and provides a written informed consent, the screening evaluations shall be performed. Subjects can be consented at any time once identified by the site study staff as potentially eligible.

If a female of child-bearing potential is found to be pregnant, or is planning to become pregnant within one week of administering the study medication, then she is not eligible for the study.

Male or female patients of at least 18 years of age are candidates for this study. If the patient may meet entry criteria, the patient will be informed about the study. The investigator should also consider the patient's risk of injury prior to screening. Even after the inclusion and exclusion criteria are reviewed, if the investigator considers the patient a risk for injury, the patient should not be enrolled in the study.

#### 12.1 Informed Consent

All patients are to give informed consent in accordance with the origins of the Declaration of Helsinki and applicable regional regulatory requirements (e.g. 21 CFR Part 50).

The patient will sign the Informed Consent Form before she/he enters the study, i.e., before screening bloods, screening assessments or any other study-related activity. The patient will be given sufficient time to consider the study's implications before deciding whether to participate. The format and content of the ICF must be agreed upon by Lakewood Amedex and the Institutional Review Board.

Should there be any amendments to the final protocol; the patient must agree to sign the amended ICF indicating that they re-consent to participate in the trial.

### 12.2 Visit 1 (Day -7 to -4 hours) - Screening

After granting of informed consent the patient will undergo screening. Screening includes the following:

- Demography data, medical history, general physical examination of all organ systems, and vital signs (blood pressure, heart rate, and temperature): Perform a physical exam and assess vital signs per hospital protocol within the specified timeframe for screening.
- Vital signs measurements: Weight, temperature, resting blood pressure, heart rate, and respiratory rate
- Hematology: WBC, RBC, Hgb, Hct, MCV, MCH, HCHC, RDW, MPV, Platelets, Neutrophils Auto % (abs), Immature Granulocyte Auto % (abs), Lymphocytes Auto % (abs), Monocytes Auto % (abs), Eosinophils Auto % (abs), Basophils Auto % (abs)
- Biochemistry: Sodium, Potassium, Bicarbonate or CO2, Chloride, Total Bilirubin,
   Creatinine, BUN, Calcium, Alkaline Phosphatase, ALT, AST, Total Protein,
   Albumin, Anion Gap, eGFR, Globulin, A/G ration
- For females of child-bearing potential: pregnancy test (urine or serum  $\beta$ -HCG) to be performed at baseline.
- Baseline Patient Disease Assessment: Visual examination of chronic ulcer, score target ulcer using DUSS Scoring System, Swab wound to culture for microbiological examination

Diabetic Ulcer Wound Scoring System (DUSS)

Parameter	Score			
Palpable Pedal Pulses	Presence = 0 Absence = 1			
Probing to Bone	$N_0 = 0$	Yes = 1		
Location of Ulcer	Toe = 0	Foot = 1		
Number of Ulcerations	Single = 0	Multiple = 1		
Score Range	0	4		

### **Diabetic Foot Ulcer Wound Infection Score**

Parameter	Wound Infection Score			
	0	1	2	3
Purulent discharge	Absent			Present
Nonpurulant drainage (serious, sanguinous)	Absent	Mild		
Erythema	None	Mild pink, barely perceptible	Moderate pale red, defined edges	Severe red to dark red
Induration	None	Mild	Moderate	Severe
Tenderness (sign)	None	Mild	Moderate	Severe
Pain (symptoms)	None	Mild	Moderate	Severe
Local Warmth (relative to uninfected contralateral foot)	Same	Mildly increased	Moderately increased	Severely increased

Photo Documentation and Calculation of the Ulcer Area and Depth using the Aranz Medical SilhouetteTM as described in Appendix A

A past medical/surgical history will be recorded for any conditions or treatments that are, in the opinion of the investigator, relevant to the current diagnosis. The previous condition will be recorded as a diagnosis rather than a previous symptom. The time of the previous diagnosis relative to the current admission will be provided (i.e., "6 months ago") to the best of the patient's knowledge. If the diagnosis was more than two years ago, then it can be recorded as "more than two years ago".

Prior medications will be recorded. Prior medications include medications that the patient is currently taken or has taken within the past fourteen days.

Physical examinations are performed at screening by the investigator or designee. The screening examinations will include general appearance, height, weight, skin, neck, eyes, ears, nose, throat, heart, lungs, abdomen, cervical and axillary lymph nodes, extremities, and nervous system. Height is measured in stocking or bare feet, and recorded in centimeters (cm). Weight is recorded in kilograms (kg).

Results of these investigations/assessments and baseline measurements obtained from the local laboratory will be reviewed by the Investigator prior to the start of the treatment. Patients who do not meet study entry criteria will be promptly notified and excluded from further participation in the study. Patients who continue to meet entry criteria will be enrolled in the study and assigned a patient number by the database. The patient can be randomized at any time following the screening.

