#### Test Kit

Test Product kits will be labelled and contain a 0.5 oz dropper bottle containing 15 mL of Test Product packaged in a cardboard carton with a foam insert for protection. These kits will be pre-labelled with kit numbers. The contents of the kits will not be known to the pharmacist, designee or clinical staff. Upon randomization of the subject, the pharmacist or designee will receive a randomization number along with a kit number that is available at that site. The kit with the corresponding kit number will be used for dose administration.

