#### **Analysis Populations**

All statistical processing will be performed using SAS® unless otherwise stated. All subjects enrolled in the study that were dispensed and applied test article at least once will be included in the analysis of safety and efficacy and will be considered the intent-to-treat (ITT) population. Last-observation-carried-forward (LOCF) will be used to impute missing values for efficacy variables.

A subject will be included in the per-protocol (PP) efficacy analysis population if all of the following criteria are met:

- Subject meets the inclusion/exclusion criteria;
- Subject has not taken or applied any interfering concomitant medications
- Subject has completed Visit 4/Day 15 (± 2 days) and has missed no more than one Follow-Up Visit;
- Subject has been compliant with the dosing regimen (i.e., subject must take at least 80% of the expected doses up to and including the final visit).

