#### 8.9 First Dose Plan

The dosing schedule for all cohorts is intended to minimize potential risk to subjects' safety. It is known that the types, severities, time courses and pharmacokinetic correlates of adverse effects observed in preclinical studies are not necessarily predictive of experience in human subjects, at any dose. This plan further recognizes that major acute toxicities of pharmaceuticals in human subjects may on rare occasions not be predicted by preclinical

experience, warranting additional caution in administering first doses to humans. As such caution has been advised in particular regarding biopharmaceuticals, it is noted that Nu-3 is not categorized as a biopharmaceutical. A traditional risk-reduction strategy has been to apply large safety factors (divisors of human equivalent doses corresponding to NOAELs in appropriate animal toxicology models) in determining the Maximum Safe Starting Dose for first-in-human study. A further risk-reduction strategy, adopted here, is to separate first and second exposures more widely in time than has been typical study procedures.

Preclinical experience suggests that possible adverse effects after a single dose topical exposure to NU-3 would be unlikely. Accordingly, the dose plan is as follows:

- Qualified patients for all Cohorts are screened from Day -7 to -4 hours. Patients understand (disclosed in informed consent) that their qualification for enrollment is not finalized until the time of enrollment. They understand that their order of enrollment is randomly determined.
- On Day -7 to -4 hours, baseline procedures are performed (demographics and medical history, and limited physical examination per protocol, urine pregnancy test (if applicable), baseline laboratory tests (blood chemistries, hematology, coagulation profile, and urinalysis), and baseline subject disease assessments).
- On Day 1, the patients is randomized and dosed to either Nu-3 or Placebo.
- On the next following day, Day 2, if the Investigator observes no dose-limiting toxicity (Section 8.10.6) in the patient dosed on Day 1, the Investigator will distribute the investigational product kit and instructed to apply the product twice daily for one (1) week (7 days).
- If the Investigator observes a suggestion of dose-limiting toxicity, the procedure specified in Section 8.10.3 is followed.

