#### **5. ANALYSIS POPULATIONS**

##### **5.1 Intent-to-Treat (ITT) Population**

All randomized subjects will be included in the ITT Population.

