## **8.2 Analysis of Efficacy Endpoints**

For each dose group, the proportion of subjects with a normal culture at the end of the MAD portion of the study will be compared to the proportion of subjects with a normal culture at the end of the MAD portion of the study for the combined placebo group using a Fisher's exact test. A subject with a normal culture at this time will be considered a success. Any subject with a missing value at the end of the MAD portion of the study will not be included in the analysis. A p-value less than 0.05 will be considered statistically significant and a p-value less than 0.0167, employing a Bonferroni correction for multiple comparisons, will be considered highly conclusive.

For continuous efficacy endpoints, data will be summarized descriptively at and a comparison using the Wilcoxon Rank Sum test between each of dose groups and the combined placebo group will be performed at each visit. For these endpoints, no imputation for missing values will be performed.

For categorical endpoints, a Fisher's exact test will be performed in a similar manner. Subjects missing a value for a secondary endpoint will be considered a failure (counted in the denominator) for that endpoint.

For all tests, a p-value less than 0.05 will be considered statistically significant and a p-value less than 0.0167, employing a Bonferroni correction for multiple comparisons, will be considered highly conclusive. Analysis for each secondary endpoint will be performed on the ITT population and the PP population.

Ulcer measurements and percentage of area reduction will be summarized descriptively by visit and statistical testing using a Wilcoxon Rank Sum test between each dose group and the combined placebo group. For all tests, a p-value less than 0.05 will be considered statistically significant. Analysis for each additional endpoint will be performed on the ITT population and the PP population.

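### Section 12.2 permits randomization up to about seven days before dosing while Section 8.9 puts it on Day 1; early randomization can create avoidable undosed ITT subjects, counted as failures on the DFI signs

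*Protocol*

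**What the plan says.** Two current passages of the protocol time randomization differently.

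- Section 12.2 (Visit 1, screening) ends, after the investigator's review of screening results, with "The patient can be randomized at any time following the screening". The introduction to Section 12 sets the window: "Subjects can be screened up to seven days to 4 hours before treatment".
- Section 8.9, whose plan covers all cohorts, says "On Day 1, the patients is randomized and dosed to either Nu-3 or Placebo". It adds that a patient's qualification is not settled until enrolment.

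The schedule of events has no row for randomization. Section 10.5 gives the block size and the kits per site, but no time point. On kits, the synopsis says "Upon randomization of the subject, the pharmacist or designee will receive a randomization number along with a kit number" and then "The kit with the corresponding kit number will be used for dose administration".

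The analysis rules that meet this subject are:

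- SAP 5.1: "All randomized subjects will be included in the ITT Population". Protocol 16.2 agrees.
- Synopsis, Analysis Populations: the subjects to whom test article was dispensed and who applied it at least once "will be considered the intent-to-treat (ITT) population".
- SAP 8.2: a subject with no culture at the end of the MAD portion leaves the culture test, and continuous endpoints are not imputed. A subject missing a categorical secondary endpoint "will be considered a failure (counted in the denominator) for that endpoint".

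**The concern.** A subject randomized on Day -5 complies with 12.2 and breaches 8.9. In the days that remain, eligibility can still change. Exclusion 7 covers a positive pregnancy test at Visit 2 as well as at screening (the current schedule of events marks no pregnancy test at Visit 2, a separate inconsistency, but the criterion stands). Exclusion 4 (antibiotics in the last seven days) and exclusion 8 (raised temperature with clinical features of infection) can also become true, and Section 12.3 retakes temperature just before treatment. These are ambulatory patients with infected ulcers, so some change or non-return before Day 1 is foreseeable.

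Such a subject is randomized, holds an assigned kit number, and is never dosed. The loss carries no information about Nu-3. Yet the plan excludes the subject from one efficacy test and fails the same subject in another, in groups small enough for one person to show. An undosed Nu-3 subject pulls the active rate down; an undosed placebo subject pulls the placebo rate down and flatters Nu-3.

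**Working it through.** The plan states no figure on this point, so there is none to reproduce. The check sets the rules side by side and then sizes the effect of one subject.

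**1. Length of the gap.** Screening opens on Day -7 and 12.2 sets no lower limit on when randomization may follow. The gap between randomization and dose can be up to about 7 days under 12.2, and is within Day 1 under 8.9.

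**2. Where an undosed randomized subject is counted** (assuming no assessment at the end of the MAD portion):

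| Rule | Treatment of the subject |
|---|---|
| Protocol 16.2, SAP 5.1 (ITT) | Included |
| Synopsis ITT | Not included |
| SAP 5.2 and 9 (safety) | Not included |
| SAP 5.3 (PP, all doses required) | Not included |
| SAP 8.2, culture | Dropped from the test |
| SAP 8.2, continuous endpoints | Contributes nothing |
| SAP 8.2, categorical secondary endpoints | Counted as failure |

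The SAP does not label its endpoints as secondary one by one. Apart from culture, the categorical ones in SAP 8.1 are the absences of the individual DFI signs.

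**3. Effect of one subject on a success proportion.** If one would-be success becomes a failure, the proportion falls by 1/n.

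- Dose group, n = 8 (Section 8.4): 1/8 = 12.5 points.
- Pooled placebo in the SAP, 3 cohorts × 2 = 6: 1/6 = 16.7 points.
- Pooled placebo in the five-cohort protocol, 5 × 2 = 10: 1/10 = 10 points.

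**4. Effect if the subject is replaced in the same arm.** Under 16.2 and SAP 5.1 the undosed subject stays in ITT, so the denominator grows by one. With s successes the fall is s/n − s/(n+1) = s/[n(n+1)], largest at s = n.

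- Dose group: 8/(8 × 9) = 11.1 points.
- Pooled placebo of 6: 6/(6 × 7) = 14.3 points.

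**5. Illustration against the SAP's threshold.** Hypothetical two-sided Fisher's exact tests on one DFI sign: 6/8 versus 0/6 gives p = 0.0097. If one active responder is instead an undosed subject counted as a failure, 5/8 versus 0/6 gives p = 0.031. The first is below the SAP's 0.0167 level; the second is not.

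**6. How often this might happen.** No document gives a rate of loss between randomization and dosing. With assumed rates q of 2%, 5% and 10%, and all 10 subjects of a cohort randomized early, the chance of at least one undosed subject is 1 − (1 − q)^10 = 18%, 40% and 65%. For the 2 placebo subjects of a cohort, 1 − (1 − q)^2 = 4%, 10% and 19%.

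**The case against.** The best defence is that 12.2 is permissive and does not instruct early randomization. It includes Day 1, and Visit 2 may fall on the screening day. The operative dosing text pairs the two steps: 8.9 does so expressly, and 8.11 speaks of randomization and dosing proceeding together. Early randomization is therefore something the plan allows, not its stated schedule. That is right, but a permitted departure with no row in the schedule of events to overrule it is still a contradiction a site can act on.

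Several stronger readings are tempting and the documents do not support them.

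- *A kit is used up.* The kit number is assigned at randomization, but the kit is used at dosing. The number is tied up; whether it can be reassigned is not stated.
- *The loss enters the efficacy denominators generally.* It reaches only the categorical secondary endpoints in ITT. The culture test and the continuous endpoints drop the subject, the PP analysis excludes the subject, and safety, the primary objective, is analysed on dosed subjects.
- *A lost placebo subject halves the control.* That holds inside one cohort of 8:2, but SAP 4 and 8.2 compare each dose with the pooled placebo group, so the subject is 1 of 6 there.
- *The 8:2 split is broken for good.* Section 9.2 allows a subject who was not dosed to be replaced, and Section 9 allows about 55 enrolled for 50 evaluable. Replacement is case by case, and matching to the same arm is not stated, so this softens the point without closing it.

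**Conclusion.** The concern stands in a limited form. Sections 12.2 and 8.9 conflict, and following 12.2 can produce avoidable randomized-but-undosed subjects who count as failures on the DFI signs in ITT. Each can move a dose group by up to 12.5 points or the SAP's pooled placebo group by up to 16.7 points (up to 11.1 and 14.3 if replaced in the same arm). These are maxima. They rest on the SAP's three cohorts, on missing data at the end of the MAD portion, and on the lost subject otherwise being a success. The 18% to 65% range rests wholly on assumed loss rates and universal early randomization, and is no forecast for this trial.

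A reader might also infer that early randomization is what makes the two ITT definitions differ, and that moving it to Day 1 would make them coincide. It would not. The definitions differ as written, and a subject randomized on Day 1 can still go undosed. The synopsis also requires dispensing, which the schedule of events places at Visit 3. Read literally, a subject who had only the Day 1 clinic application is outside the synopsis ITT set but inside that of 16.2 and SAP 5.1.

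The effect is modest in a pilot with no sample size calculation, but the correction is nearly free and worth making.

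**What to change.** 1. Delete the randomization sentence at the end of 12.2. State in 10.5, 12.2 and 12.3, and as a row in the schedule of events, that randomization takes place at Visit 2 (Day 1), after eligibility is rechecked and immediately before the first application. This is what 8.9 already says.
2. Separately, replace the synopsis ITT definition so that it agrees with 16.2 and SAP 5.1. Because the synopsis uses that one set for both safety and efficacy, its safety set then needs its own line.
3. In one sentence, say how a randomized-but-undosed subject and the assigned kit number are handled, including the arm of any replacement.

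The cost is a protocol wording change with the usual ethics committee approval. Kits are already held at the sites, so assignment on Day 1 needs no extra supply step, and the SAP's ITT definition can stay as it is.

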### 12.3 Visit 2 (Day 1) SAD Treatment

Patients will return after the screening visit for Single Ascending Dose Treatment. Patient disease assessments will be performed as specified in the schedule of events table.

- Vital signs (blood pressure, heart rate, temperature) will be examined within 10 minutes prior to the start of treatment
- Baseline Patient Disease Assessment: Visual examination of chronic ulcer, score target ulcer using DUSS Scoring System, Swab wound to culture for microbiological examination Not applicable if Visit 2 is the same day as Screening Visit
- Photo Documentation and Calculation of the Ulcer Area and Depth using the Aranz Medical SilhouetteTM system - Not applicable if Visit 2 is the same day as Screening Visit

In SAD Treatment, eligible patients will be treated with a single application of Test Product. Test Product will be administered to the infected diabetic foot ulcer and surrounding intact skin at a dose of 1 to 3 drops from a dropper bottle per 1 cm^2 of ulcer area, left open to air for 5 minutes and then dressed using Owens gauge, Kerlex and tape. The ulcer with a non-abrasive bandage following the initial observation period and the patient will be released with verbal instructions to leave the bandage on the wound and return for a follow up visit within  $24 \text{ h} \pm 2 \text{ h}$ .

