#### Administration

Test Product will be administered to the infected diabetic foot ulcer and surrounding intact skin at a dose of 3 drops from a dropper bottle per 1 cm2 of ulcer area. This will be explained to test subjects so they know the exact number of square

After application of the Test Product is complete, the wound will be left open to air for 5 min and then will be dressed as per the following: Owens Gauze will be trimmed to cover the entire dimension of the ulcer and overlaid into the ulcer. Gauze dressings (2 x 2 inches) will be placed over the Owens Gauze to a depth of 1/4 inch followed by a circumferential wrap of 2 inch Kerlex. The dressing will be secured with paper tape applied to the circumferential dressing as to not come in contact with the underlying skin.

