- Baseline Subject Disease Assessment: Visual examination of chronic ulcer, score target ulcer using DUSS Scoring System, Swab wound to culture for microbiological examination – Not necessary if Visit 2 is the same day as Visit 1
- Photo Documentation and Calculation of the Ulcer Area and Depth using the Aranz Medical Silhouette™
   System Not necessary if Visit 2 is the same day as Visit 1

In SAD Treatment, eligible subjects will be treated with a single application of Test Product. Test Product will be administered to the infected diabetic foot ulcer and surrounding intact skin at a dose of 3 drops from a dropper bottle per 1 cm $^2$  of ulcer area, left open to air for 5 minutes and then dressed using Owens gauge, Kerlex and tape. The ulcer with a non-abrasive bandage following the initial observation period and the subject will be released with verbal instructions to leave the bandage on the wound and return for a follow up visit within 24 h  $\pm$  2 h.

Visits 3 (Day 2 [24 h  $\pm$  2 h.]) MAD Treatment: Subjects will return after the Single Ascending Dose Treatment. Subject disease assessments will be performed as specified in the schedule of events table.

- Vital signs (blood pressure, heart rate, temperature) will be examined within 10 minutes prior to the start
  of treatment
- Baseline Subject Disease Assessment: Visual examination of chronic ulcer, score target ulcer using DUSS
   Scoring System, Swab wound to culture for microbiological examination

The Principal Investigator will visually exam the chronic ulcer to determine if a subject is eligible to continue in the study. Eligible subjects will be provided with his/her designated test product kit and instructed to apply the product twice daily for one (1) week (7 days). Test product application will be demonstrated, and subject instruction sheet reviewed, using the assigned test product. The subjects will be observed applying the first dose in the clinic to ensure compliance (administering Test Product to the infected diabetic foot ulcer and surrounding intact skin at a dose of 3 drops from a dropper bottle per 1 cm^2 of ulcer area, left open to air for 5 minutes and then dressed using Owens gauge, Kerlex and tape.). The subject will be scheduled for the next follow-up visit, with a reminder to bring the test article kit to the visit.

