#### 8.3 Cohorts

The dose of Nu-3 administered will be escalated in five planned sequential cohorts, with 10 subjects in each cohort, to be administered Placebo (0.9% saline) or Nu-3 doses of 0.1% solution of BisphosphocinTM Nu-3 in 0.9% saline (w/v) (Cohort 1), 1% solution of BisphosphocinTM Nu-3 in 0.9% saline (w/v) (Cohort 2), 2% solution of BisphosphocinTM Nu-3 in 0.9% saline (w/v) (Cohort 4), 10% solution of BisphosphocinTM Nu-3 in 0.9% saline (w/v) (Cohort 5) at twice daily for 7 consecutive days.

Additional cohorts may be enrolled, if needed, as provided by protocol.

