### 8.10.5.3 Definition of Maximum Tolerated Dose (MTD)

If dose escalation is stopped according to criteria of 8.10.4 and the Safety Review Committee does not decide to administer a dose lower than the level at which dose escalation was stopped and higher than the next lowest tested level, the next lowest tested level will be considered the maximum tolerated dose (MTD).

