#### 10.8 **Study Drug Administration**

### 10.8.1 Study Drug Administration Procedure

Licensed Clinical Operations personnel at the investigative site administer each dose of Study Drug to study. Test Product will be administered to the infected diabetic foot ulcer and surrounding intact skin at a dose of 3 drops from a dropper bottle per 1 cm^2 of ulcer area.

After application of the Test Product is complete, the wound will be left open to air for 5 min and then will be dressed as per the following: Owens Gauze will be trimmed to cover the entire dimension of the ulcer and overlaid into the ulcer. Gauze dressings (2 x 2 inches) will be placed over the Owens Gauze to a depth of 1/4 inch followed by a circumferential wrap of

2 inch Kerlex. The dressing will be secured with paper tape applied to the circumferential dressing as to not come in contact with the underlying skin.

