### 16.2 Analysis Populations

All randomized subjects will be accounted for in a listing for subject disposition. All randomized subjects will be included in the intent-to-treat (ITT) population. All subjects administered any amount of investigational product will be included in the Safety population. The per-protocol (PP) population will include all subjects who meet enrollment criteria and receive all doses of investigational product as required by the protocol and who have no major protocol violations. Major protocol violations are defined as follows:

- 1. Failure to properly obtain consent or subject not consented prior to dosing.
- 2. Subject not meeting the entry criteria and enrolled without a written waiver.
- 3. Subject randomized in the incorrect treatment arm.
- 4. Subject given incorrect dose (overdose/under-dose).
- 5. Data not available from the post-dose central laboratory assessment.
- 6. Failure to complete the study.
- 7. Performing study procedure(s) not described in the approved protocol.

All safety and efficacy analyses will be performed on all populations.

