## 3. STUDY OVERVIEW

This is a phase 1/2a prospective, multi-center, blinded, randomized, dose escalation study. This study will be conducted at four investigational sites. Subjects with diabetic chronic foot ulcer(s) and a Diabetic Ulcer Severity Score (DUSS) of 0 to 3, ulcerated area(s) of not more than two ulcers between 0.5 and 6 cm^2, and no underlying DUSS Probing to Bone='Yes' are eligible to be enrolled into the study.

Doses of Nu-3 will be escalated in three planned sequential cohorts with 10 subjects in each cohort. Randomization will be 4:1 active to placebo in each cohort. The dose levels in each cohort are:

- Cohort 1 – 0.1% solution of Nu-3 in 0.9% saline with vehicle
- Cohort 2 – 1% solution of Nu-3 in 0.9% saline with vehicle
- Cohort 3 – 2% solution of Nu-3 in 0.9% saline with vehicle

Each cohort has placebo defined as 0.9% saline with vehicle. Dosing will be twice daily for 7 consecutive days.

Subjects will have scheduled study visits as follows:

- Screening (Day -7 to -4 hours)
- Single dose visit (Day 1)

- Safety review and multiple dose visit (Day 2)
- Safety review visit (Day 9  $\pm$ 1 day)
- Final Visit (Day 15  $\pm$ 2 days)

At the conclusion of each cohort, a Safety Review Committee will review the safety data and determined if it is safe to proceed to the next cohort. The committee includes, but is not limited to the Sponsor's designated Medical Monitor, the Medical Director of the CRO, and the Medical Director of Lakewood Amedex. Additional members can be added as the sponsor deemed appropriate.

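### The protocol gives two drop rates for the same Day 1 and Day 2 applications, so the amount of Nu-3 per cm² can overlap or reverse between subjects in adjacent cohorts

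*Protocol*

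**What the plan says.** Three parts of the current protocol fix the rate:

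- Synopsis, Administration: "at a dose of 3 drops from a dropper bottle per 1 cm2 of ulcer area".
- Synopsis, Clinical investigation Procedure, with the same rate for Visit 2 and Visit 3. For Visit 3 the subject is watched "administering Test Product to the infected diabetic foot ulcer and surrounding intact skin at a dose of 3 drops from a dropper bottle", again per cm².
- Section 10.8.1: "surrounding intact skin at a dose of 3 drops from a dropper bottle per 1 cm"².

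Two parts give a range for the same two applications. Section 12.3 (Visit 2, Day 1) has "surrounding intact skin at a dose of 1 to 3 drops from a dropper bottle per 1 cm"², and section 12.4 (Visit 3, Day 2) repeats that wording.

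Dose levels are named by concentration. Protocol section 8.3 states: "The dose of Nu-3 administered will be escalated in five planned sequential cohorts". The synopsis gives the five levels as 0.1%, 1%, 2%, 5% and 10%. The SAP, section 3, covers fewer: "Doses of Nu-3 will be escalated in three planned sequential cohorts with 10 subjects in each cohort", at 0.1%, 1% and 2%.

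Two rules depend on dose being well defined. If escalation stops and no intermediate dose is tried, section 8.10.5.3 says "the next lowest tested level will be considered the maximum tolerated dose (MTD"). Section 16.2 lists as a major violation "Subject given incorrect dose (overdose/under-dose").

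**The concern.** The two texts govern the same visits, and a site can comply with one while departing from the other. With two to four sites, practice may differ between them. The Visit 3 rate carries most weight, because it is the one shown to subjects before a week of twice-daily application at home. The home treatment log (Appendix B) records date and time, initials, footwear and comments, but not drops, so the rate used at each home application cannot be read from it.

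Only concentration is fixed by cohort. If the drop rate may vary 3-fold, each dose level covers a 3-fold range of Nu-3 per cm². Section 8.8 describes this as a first-in-human study. Under section 8.10.5.1, two DLTs among a cohort's active subjects stop escalation and one expands the cohort. Those counts, the MTD and the secondary objective on dose range all attach to the dose level, so a loosely defined level weakens what they mean.

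The conflict also reaches the per-protocol population. A subject given 1 or 2 drops per cm² complies with sections 12.3 and 12.4 but not with section 10.8.1, and the violation rule does not say which is the reference.

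**Working it through.** The documents give no applied-amount figure to reproduce, so this is direct arithmetic.

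**Inputs.** Concentrations are 0.1, 1, 2, 5 and 10% (synopsis, Randomization). Drop rate is 3 per cm² (synopsis, section 10.8.1) or 1 to 3 per cm² (sections 12.3 and 12.4). Drop volume is not stated. It is assumed equal for all bottles and solutions, so it cancels from every comparison.

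**Formula.** Relative amount per cm² = concentration (%) × drops per cm².

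| Cohort | At 1 drop | At 3 drops |
|---|---|---|
| 0.1% | 0.1 | 0.3 |
| 1% | 1 | 3 |
| 2% | 2 | 6 |
| 5% | 5 | 15 |
| 10% | 10 | 30 |

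**Adjacent steps: lower cohort at 3 drops against the next at 1 drop**

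| Step | Concentration ratio | Lower ÷ higher | Reversal possible? |
|---|---|---|---|
| 0.1% to 1% | 10 | 0.3 ÷ 1 = 0.3 | No |
| 1% to 2% | 2 | 3 ÷ 2 = 1.5 | Yes |
| 2% to 5% | 2.5 | 6 ÷ 5 = 1.2 | Yes |
| 5% to 10% | 2 | 15 ÷ 10 = 1.5 | Yes |

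A step can reverse when its concentration ratio is below 3. That is three of the four steps in the protocol and one of the two in the SAP (1% to 2%).

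**Non-adjacent cohorts.** At the closest approach, lower at 3 drops against higher at 1, the values are 0.3 v 2, 3 v 5 and 6 v 10. None overlap.

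**How often.** The documents do not describe practice, so these are assumptions. Each takes one random subject from each of two adjacent cohorts, with rates chosen independently, in the three steps that can reverse.

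- All subjects at 3 drops: 0.
- Whole drops, with 1, 2 and 3 equally likely: of the 9 drop pairs only (3, 1) reverses, giving 1/9. For 1% v 2% and 5% v 10% the pair (2, 1) ties, a further 1/9.
- A share p at 3 drops and the rest at 1, in both cohorts: p(1 − p). This is 0.19 at p = 0.25 or 0.75, and 0.25 at p = 0.5.
- Rate continuous and uniform from 1 to 3: 1/16 for the 2-fold steps and 1/80 for the 2.5-fold step.

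**Cohort means.** With 1, 2 and 3 drops equally likely, the mean is 2 drops. The cohort means are then 0.2, 2, 4, 10 and 20, still in order.

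**With one common fixed rate.** Amounts per cm² keep the concentration ratios of 10, 2, 2.5 and 2, and no cohorts overlap. This holds for any single rate.

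**The case against.** The strongest objection is that the protocol defines and escalates dose by concentration, and concentration rises in order under either text. Amount per cm² is this review's measure. Cohort means stay ordered when both cohorts use the same mix of rates, three drops satisfies every section, and no placebo comparison reverses. All of this stands. It limits the consequence but leaves the two instructions in conflict. The protocol also calls the drop rate itself a dose in each of these places.

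The reversal frequencies depend on the model. Drops are counted over a whole ulcer of 0.5 to 6 cm², so rates per cm² need not be whole numbers, and the continuous version gives only 1/16 and 1/80. These lie within the 0 to 1/4 range, which is illustrative and not a prediction.

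Area-based dosing already spreads total exposure. At a fixed 3 drops, a 6 cm² ulcer at 1% receives 6 × 3 × 1 = 18 relative units, against 0.5 × 3 × 10 = 15 for a 0.5 cm² ulcer at 10%. That is correct for total amount. It does not justify a further 3-fold spread in amount per cm².

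Other records exist: amounts administered (protocol section 10.4.2), product collected at Visit 4 (section 12.5), and SAP listings of in-clinic administration and drug return (16.2.6.1 to 16.2.6.3). The SAP also settles per-protocol membership before unblinding (section 5.3). These may help describe use afterwards. They neither set the rate nor define under-dosing between 1 and 3 drops.

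Finally, the subject instruction sheet is not among the documents, and the synopsis sentence on explaining the dose to subjects breaks off. The sheet may state a home rate. The contradiction between the protocol sections would remain.

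**Conclusion.** The point holds and should be fixed before the protocol is used. It is an internal inconsistency in a dosing instruction. Older protocol versions in the same file use 1 to 3 drops, but the conflict lies wholly within the current text.

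If both texts are followed, individual subjects in a lower cohort can receive 1.2 to 1.5 times the amount per cm² of subjects in the next, in three of four protocol steps and one of two SAP steps. This rests on equal drop volume across bottles and on amount per cm² as the measure. Its frequency is unknown and would be zero if every site used 3 drops. The consequence is confined to the meaning of DLT counts, the MTD and the dose-range objective, and to per-protocol classification from 1 to below 3 drops. Exactly 3 drops, more than 3, and fewer than 1 can all be classified under both texts.

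**What to change.** Reconcile the synopsis (Administration, and the Visit 2 and Visit 3 text), section 10.8.1, and sections 12.3 and 12.4 to one application-rate instruction. State the same instruction in the subject instruction sheet, and name it as the reference for the overdose/under-dose violation in section 16.2. The choice of rate is the sponsor's.

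As an optional addition, put a drops-applied column in the home treatment log so that the rate actually used can be reported by cohort.

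The cost is wording in two to five places and, if adopted, one log column. No extra subjects, visits or procedures are needed.
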